Therefore, the third subproject of this proposal is focused on the implementation of outcome measurement tools to improve the efficacy, effectiveness and the real utility of the ATD developed. On the other hand, it is also very important to assess the functional impact the ATD has on user's participation in their social environment. For that, other measurement tools to assess functional mobility outcomes will also be also carried out during basal assessment and after 6 months of ATD implementation. The mentioned tools include (all in their Spanish adapted version) the Six-minute Walk Test (17,18), 10 Meter Walk Test (19), Pediatric Balance Scale (20), and the Functional Independence Measure (FIM) (21,22). The measurement tools will be carried out depending on the characteristics of the ATD and the targeted population.

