**Procedure:**

The performance of MATCH subproject will be conditioned by the advance of other two subprojects. Nevertheless, in the schedule (see below) is showed how the different tasks are related to each other, and how the development of the complete project will be in the timeline.

The tasks that will be done in the MATCH subproject contemplates several consecutive phases:

1. Planning of assessment process: The research group defines the study variables and measure instruments to obtain the data. Those tools will allow to determine the needs, capabilities, priorities and expectations of participants, with respect to the use of AT.
2. Contact with the collaborators centers and presentation of the project: The members of each research group will contact with the collaborators centers (specified in sections before) to present the characteristics of the project, to get its authorization and, at the time, to give all information of the users, potential participants.
3. Selection of participants and process of informed consent: According to the inclusion criteria, the participants will be recruitment of each collaborator center, and the information form will be given to them. After the reading, participants will offer their informed consent to involve in the research.
4. Initial assessment: In this phase the evaluation of the participants will be done, with the application of the instrument presented in table 1. According to the age of the person, specific questionnaires will be used to gather information more concrete about the skills for mobility. This assessment will allow determining the specific needs, demands and capabilities of participants. The assessment process will be done by professionals of research group in rooms of collaborators centers.
5. Technical advice to the development of the other subprojects (AIRPLANE and AAI): According to the obtained results from initial assessment and after the analysis of first data, the research group of UDC will inform to the groups of UAH and US the main findings. That data will be taken into account and incorporated to the technical development of the AT. Only in this way, it will generate viable and adequate products to the detected needs previously, and this assistive technology that integrates the robotic and AI models answer correctly to these demands.

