6. Check of functioning and adaptation of assistive technology to the requirements of people with disabilities: The research group of UDC will verify the components of assistive technology in terms of usability and universal design, and its adequacy to the specifications identified in the previous phase. That process will be a collaborative task, in which will participate the members of research group and the professionals of collaborator centers, not implicating a direct intervention with the users.

7. Implementation of AT in the daily life of participants: The professionals of collaborator centers, supported by the research groups, will carry on the training in the use of AT by the participants, facilitating its incorporation during the performance of activities of daily living.
8. Determination of possible improvements in the assistive technology, derived by the experience of participants: The members of research group will test the AT in the context of people with disabilities, detecting and registering the possible lacks and improvements that the device would need to get the best match between the AT and the user.
9. Application of outcome measures and analysis of the data: After the process of implementation of AT (the next 2 and 6 months), members of research group and the professionals of collaborators centers will apply the measure instruments to determine the possible improvements in the level of functional independence (FIM scale) of people with disabilities, the impact that the AT has had on their lives (PIADS scale) and the level of matching between person and AT (ATD PA – MPT model). The data will be analysed in descriptive and inferential terms, establishing the respective comparison with the obtained results of initial assessment.
10. Elaboration of explicative model or protocol: The obtained results from the use of AT by the participants, and its posterior analysis will allow to determine the influent factors that would be able to facilitate or restrict the good and efficient use of this device. That will be the best solution to demonstrate the efficacy and efficiency of AIR4ALL and its final goal to improve the participation and quality of life of people with disabilities.

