**Data analysis:**

The quantitative variables will be expressed as Mean (M) and Standard Deviation (SD), including range, minimum and maximum values. Apart from the simple description of data and variables, inferential analysis will be done to determine possible significant relationships and correlations between study variables or that allows to the contrast of hypothesis.

Shapiro Wilk and/or Kolmogorov – Smirnov will be applied to determine if the sample meets with the normal distribution criteria, and to decide the type of statistical test that will be implemented (parametric or no-parametric).

The T- student paired test or the U-Mann Whitney will be applied to establish the possible differences of means, according different dicotomic variables, in the assessment scales of FIM, PIADS, Walk tests and level of matching person – AT. The ANOVA test or Kruskal – Wallis will be used in the cases of polycotomic variables, to establish possible differences of means between results of the scales.

The association of numeric variables will be analysed by Pearson or Spearman correlation test, according to distribution of the sample. To evaluate the association of categorical variables, chi-square will be applied, or likelihood ratio if the observed frequencies are lower than 5%.

To check the differences between related samples, with repeated measures (in the case of FIM scale and the scales of mobility – initial assessment and in the follow-up of 2 and 6 months), the t-student test or the Wilcoxon ranges will be used, according correspond to the sample distribution.

The analysis of the data will be done with the program SPSS v.24 for Windows. The level of significance to do the contrast of hypothesis is established to 5%.

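### FIM and mobility change is tested from an assessment made before the device is finished and in use, so in one growing cohort it cannot by itself show device efficacy

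*Protocol*

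**What the plan says.** **Order of work.** The Procedure (section 4) states: "The tasks that will be done in the MATCH subproject contemplates several consecutive phases". Phase 4 is the initial assessment. In phase 5 its findings go to the two technical groups: "That data will be taken into account and incorporated to the technical development of the AT". Phase 6 checks and adapts the device, "not implicating a direct intervention with the users". Phase 7 brings it into daily life, with training. The deliverables in section 6 keep this order: T2 initial assessment, T3 prototype improvements, T4 implementation sessions.

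**Follow-up and comparator.** Phase 9 applies the outcome measures "After the process of implementation of AT (the next 2 and 6 months" (FIM, PIADS and ATD PA are named) and then fixes the reference: "The data will be analysed in descriptive and inferential terms, establishing the respective comparison with the obtained results of initial assessment". Data analysis repeats this for the repeated measures, "in the case of FIM scale and the scales of mobility – initial assessment and in the follow-up of 2 and 6 months", using a paired t-test or Wilcoxon test at the 5% level.

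**A different schedule.** The Background (section 2) says that the functional mobility tools, among which it lists FIM, are "carried out during basal assessment and after 6 months of ATD implementation".

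**Use of the results.** Phase 10 says that the results and their analysis will serve to "demonstrate the efficacy and efficiency of AIR4ALL and its final goal to improve the participation and quality of life of people with disabilities".

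**Design and population.** The design is a pilot longitudinal cohort, and no comparison group is described. Participants are 2 to 21 years old, with a disability arising from disease or a permanent health status.

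**The concern.** Follow-up is counted from implementation, but change is counted from the initial assessment. The two starting points are separated by however long it takes to finish and check the device. The Procedure makes MATCH depend on the progress of the other two subprojects, so a delay there lengthens the separation.

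Children gain function as they grow, and some of the qualifying conditions may progress. On FIM and the walking and balance tests, a device with no effect could therefore appear to help because participants grew while it was being finished. A useful device could look useless because participants declined in that time. The test answers what has changed since the first assessment, not what has changed since the device came into use. The Abstract names independence and functional mobility among the project's aims, so these scales will be read as part of the evidence on whether the device works.

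**Working it through.** The protocol gives no sample size, effect size, SD or gap length for this comparison, so there is no planned figure to reproduce.

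**Step 1. Which interval is tested.** Let g be the months from the initial assessment to the start of phase 7, m the months of implementation before the follow-up clock starts, and f the follow-up (2 or 6 months).

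- Interval tested = g + m + f.
- Share without the device = g / (g + m + f).

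The order of phases makes g greater than zero. Its length is not in the visible text, because Table 1 and the schedule figure are not shown. The values of g and m below are assumptions.

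| g | m | 6-month comparison | 2-month comparison |
|---|---|---|---|
| 3 | 0 | 3/9 = 33% | 3/5 = 60% |
| 6 | 0 | 6/12 = 50% | 6/8 = 75% |
| 12 | 0 | 12/18 = 67% | 12/14 = 86% |
| 6 | 3 | 6/15 = 40% | 6/11 = 55% |
| 12 | 3 | 12/21 = 57% | 12/17 = 71% |

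The 2-month column applies only if there is such a visit (step 4).

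**Step 2. Background change under linear drift.** Compared with measuring from the start of phase 7, the background part of the mean change is multiplied by (g + m + f) / (m + f). For f = 6 and m = 0 this gives 9/6 = 1.5, 12/6 = 2 and 18/6 = 3 at gaps of 3, 6 and 12 months. These multiples do not depend on sample size, SD or correlation.

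**Step 3. Rejection rates, for illustration only.** Assume no device effect, n = 30, drift of 0.1 SD per 6 months, and a two-sided 5% paired t-test at 6 months. The SD of the difference is sqrt(2(1 − rho)) in baseline-SD units. Rho is 0.6 to 0.8 from phase 4 and 0.8 to 0.9 from phase 7. Power is from the noncentral t distribution with noncentrality sqrt(n) × drift / SD of the difference.

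| g | m | Drift from phase 4 | Rejects from phase 4 | Drift from phase 7 | Rejects from phase 7 |
|---|---|---|---|---|---|
| 3 | 0 | 0.15 SD | 14–24% | 0.10 SD | 13–22% |
| 6 | 0 | 0.20 SD | 22–39% | 0.10 SD | 13–22% |
| 12 | 0 | 0.30 SD | 43–71% | 0.10 SD | 13–22% |
| 6 | 3 | 0.25 SD | 32–55% | 0.15 SD | 24–43% |

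At a 3-month gap the two baselines barely differ. Allowing 3 months of implementation, the later baseline itself rejects in 24–43%, because growth during use remains.

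**Step 4. Visit times.** The Background gives baseline and 6 months for FIM and the mobility tests. Data analysis gives initial assessment, 2 and 6 months. Phase 9 gives 2 and 6 months and names FIM but not the mobility tests. These do not agree.

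**The case against.** The strongest reply is about target and weight.

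- **The efficacy sentence is not attached to the FIM test.** It stands in phase 10, on the explanatory model, and covers the results as a whole. For FIM, phase 9 speaks only of possible improvements. This stands. A reader might infer that the protocol rests its efficacy claim on the FIM and mobility tests alone, but it does not say so. What remains is that FIM is among the results drawn on, and its part cannot by itself carry that wording.
- **The main objectives lie elsewhere.** They are psychosocial impact and person–technology match, measured by PIADS and ATD PA. This also stands, and nothing here extends to those two instruments.
- **It is a pilot, and early assessment belongs to user-centred design.** Phase 4 is needed to shape the device. That justifies the assessment, but not its use as the only reference for a claim about the device. The pilot label lowers the weight of the point, but it sits poorly with wording about demonstrating efficacy.
- **The gap may be short.** Development may already be under way at phase 4, and the schedule figure is not visible. This limits the size of the problem. It does not remove it, since Data analysis names the initial assessment as the comparator.
- **A SAP could adjust for age or elapsed time.** In a single cohort, that would not separate the device from background change.

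**Conclusion.** The point holds within limits. For FIM and the mobility scales, the plan tests change from an assessment that precedes completion and use of the device, in one cohort of growing participants without a comparison group. The result mixes background change over an unstated period with the period of use, and it cannot by itself support an efficacy statement.

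Only the existence of the gap is established, not its length. The shares of 33%, 50% and 67% rest on assumed gaps of 3, 6 and 12 months and no implementation time.

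Two stronger readings are not supported. A reader might take the rejection rates as an expected false-positive rate, but sample size, drift, correlation and gap are all assumed, and for short gaps the rates are close to those from a later baseline. A reader might also conclude that a new baseline at phase 7 is required. It would cost an extra session per participant and would leave growth during use in place, so the point does not depend on it.

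The conflict between the Background and Data analysis on visit times is real. The stated 36 months against July 2020 to April 2023 (6 + 12 + 12 + 4 = 34 months, counted inclusively) is clerical and carries no weight here.

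**What to change.** 1. In phases 9 and 10 and in Data analysis, add wording such as: *The FIM and mobility comparisons describe change since the initial assessment. They include time before the device was in use and are not by themselves evidence of device efficacy.* Report that change by age and by months from initial assessment to implementation and to each follow-up, without claiming that this removes the confounding.
2. Reconcile the Background (baseline and 6 months) with Data analysis (initial assessment, 2 and 6 months) on when FIM and the mobility tests are taken, and bring phase 9 into line.

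The cost is wording and one descriptive table. Deliverable T4 already registers the implementation sessions, so elapsed time needs only the assessment dates in addition. The downside is a more modest functional claim. The 36- versus 34-month mismatch can be corrected in the same edit.

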### 3. Objectives and initial hypothesis

The global project is a multi-disciplinary and cross-border research, where the **main research objective consists in the development of novel AI and computer vision based robotic solutions with advanced mobility and human-robot wearable interaction capabilities, to improve the independence and stimulation of people with disabilities.**

The general objective of this project is based on the hypothesis that the application of Information and Communication Technologies (ICTs) and AI can improve the quality of life and independence in the group of people with disability by providing support platforms to enhance the participation in activities of daily life and in their communities.

Overall, with the coordinated research we will address the following open questions:

- What techniques can be proposed from the perspective of artificial intelligence and computer vision to provide effective solutions for people with functional diversity?
- What are the challenges posed by human-robot interaction, using accompaniment platforms and wearable devices, with people with disabilities?
- How should we approach evaluation and consultancy for the design of robotic solutions as assistive technologies, so that we can guarantee an efficient and correct matching between person and technology?

In concrete, for this study protocol, the second hypothesis is related to the relevance of the assessment of the interaction between the users and the AT: in order to guarantee a high match person-AT, to also get a positive psychosocial impact in the life of people with disabilities, the assessment and monitoring result two fundamental aspects.

According to this hypothesis, the research groups has fixed two main objectives for the MATCH subproject:

- To determine the psychosocial impact of AT created during the coordinated project (AIR4ALL) on the life of people with disabilities.
- To promote the best match between the user and the assistive technology used.

To complete, few secondary goals have been proposed:

- To assess the functional skills and abilities of people with disabilities, and to identify their needs to get independence in mobility and activities of daily living.
- To design and create the best technology solutions individualized for each person, meeting with the design for all principles, and promoting the involvement of the final user.

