**Variables and Instruments:**

The study variables and the measure instruments correspondent are specified in Table 1.

The use and the application of each instrument is conditioned by the stage of intervention process, that is defined and described in the next section. All instruments have been translated and validated into the Spanish context.

The access to the clinic history of the participants won't be required to the performance of this project.

Nevertheless, all obtained results will be codified and manage through the **REDAP Platform**, that allows the capture of electronic data in the design of research database

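### PIADS, the measure for the first main objective, can have no baseline for the project device, and the inferential tests that reach it do not address the level of impact

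*Protocol*

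**What the plan says.** Section 3 gives the first of two main objectives as "To determine the psychosocial impact of AT created during the coordinated project (AIR4ALL) on the life of people with disabilities".

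In the Procedure, the initial assessment is phase 4, done "with the application of the instrument presented in table 1". In phase 5 its results go to the technical teams: "That data will be taken into account and incorporated to the technical development of the AT". Participants first use the device in phase 7, "Implementation of AT in the daily life of participants". Phase 9, at 2 and 6 months after implementation, applies FIM for functional improvement, PIADS for "the impact that the AT has had on their lives (PIADS scale") and ATD PA for the match between person and device. It closes with "The data will be analysed in descriptive and inferential terms, establishing the respective comparison with the obtained results of initial assessment" and makes no exception for any of the three.

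Data analysis provides:

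- mean, SD, range, minimum and maximum for quantitative variables;
- a t-test labelled paired, or Mann-Whitney, for differences by dichotomous variables, naming FIM, PIADS, the walk tests and the person–AT match;
- ANOVA or Kruskal-Wallis for variables with more than two categories, and Pearson or Spearman correlation for numeric variables, both stated as general rules;
- t-test or Wilcoxon for related samples at the initial, 2-month and 6-month assessments, given for FIM and the mobility scales.

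Variables and Instruments adds: "The use and the application of each instrument is conditioned by the stage of intervention process".

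**The concern.** PIADS is the instrument for a main objective, and phase 9 appears to promise a before/after inference that cannot be made for the device in question. The tests that Data analysis does direct to PIADS ask whether impact differs between kinds of participant or goes with some other variable. They do not ask how large the impact is.

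Two consequences follow. The p-values planned for PIADS could be reported as evidence on the first main objective when they say nothing about it. And an analyst who takes phase 9 literally would either find no PIADS baseline or use a rating of some other device, which is a different quantity.

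**Working it through.** The protocol at hand states no sample size, SD or expected effect for PIADS, so there is no figure to reproduce. The check is of sequence and of what each test responds to.

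**1. Can a baseline exist?** The Procedure calls its phases consecutive. Assessment (phase 4) comes before development informed by it (phase 5), which comes before use by participants (phase 7). At phase 4 the project AT has had no impact to rate. Table 1 is not in the text at hand, so an initial PIADS for a device already in use cannot be excluded, but it would not be a baseline for the project AT.

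**2. Which inference reaches PIADS?**

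| Rule in Data analysis | PIADS named? | Question answered |
|---|---|---|
| t-test or Mann-Whitney by dichotomous variables | Yes | Do two subgroups differ? |
| ANOVA or Kruskal-Wallis | No, general rule | Do several subgroups differ? |
| Pearson or Spearman | No, general rule | Is the score associated with another variable? |
| Related-samples t or Wilcoxon | No; FIM and mobility scales given | Change over time |

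The first row is called a paired test, but its alternative, Mann-Whitney, is for independent groups and the comparison is by a dichotomous variable. It is therefore between-group.

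**3. Do these tests respond to a common impact?** Add a constant c to every PIADS score.

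- Two-sample t: (mean₁ + c) − (mean₂ + c) = mean₁ − mean₂, and the SDs are unchanged.
- ANOVA and Pearson: every term is a deviation from a mean, so c cancels.
- Mann-Whitney, Kruskal-Wallis and Spearman: the ranks are unchanged.

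Every p-value is the same whether the shared impact is nil or large. This is algebra and needs no assumption about n or SD.

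**4. Illustration only.** Assumed: normal data, SD 1, two-sided 5%, equal subgroups, grouping and covariate unrelated to PIADS, and 0 standing for no impact. There were 20,000 samples (4,000 for Mann-Whitney), drawn afresh for each row. Rejection rates:

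| n | Mean impact (SD) | Two-sample t | Mann-Whitney | Pearson | One-sample t |
|---|---|---|---|---|---|
| 20 | 0 | 4.7% | 3.8% | 4.9% | 4.9% |
| 20 | 0.5 | 4.9% | 4.7% | 4.9% | 56% |
| 20 | 1.0 | 4.8% | 4.9% | 4.6% | 99% |
| 40 | 0 | 5.1% | 5.1% | 5.2% | 5.1% |
| 40 | 0.5 | 4.9% | 4.5% | 5.1% | 87% |
| 40 | 1.0 | 4.6% | 4.9% | 5.1% | 100% |

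The between-group and correlation columns stay near 5% by construction; small differences are simulation error.

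**5. What an interval would add.** The 95% CI half-width for the mean, in SD units, is t(0.975, n − 1)/√n. For assumed n:

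- n = 10: 2.262/3.162 = 0.72
- n = 20: 2.093/4.472 = 0.47
- n = 30: 2.045/5.477 = 0.37
- n = 40: 2.023/6.325 = 0.32

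Over this range the mean alone leaves uncertainty of about a third to nearly three quarters of an SD unstated.

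**The case against.** Phase 9 is a procedural summary, while Data analysis is the operative text and rightly leaves PIADS out of the repeated-measures comparison. The word respective, with the rule that instruments depend on the stage, can be read as limiting the baseline comparison to scales that have one. The objective is to determine impact, with no threshold, and in a pilot cohort a mean with SD may be enough. Intervals and reference values are often left to a statistical analysis plan.

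Much of this stands. A reader might infer that the two sections flatly contradict each other; the wording allows a reading on which they agree. A reader might infer that the level of impact goes unreported; the planned mean, SD and range do describe it. A reader might infer that the protocol assigns correlations to PIADS by name; it does so only through a general rule. A reader might infer that a test against zero is required; the documents give no no-impact value for PIADS, so that cannot be insisted on.

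What remains is that, on the reading that reconciles the sections, PIADS has no inference on its level, although phase 9 promises inferential analysis. The protocol is not silent here: it names a test for PIADS, and that test does not fit the objective. A later analysis plan could add an estimate but would leave the phase 9 sentence in place.

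**Conclusion.** The point holds in bounded form and should be fixed. No initial-assessment value of PIADS can exist for the project AT, and phase 9 does not say so. The one inferential test that names PIADS is between-group and mislabelled as paired. Neither it nor the general rules that may also apply can detect an impact shared by all participants. The first main objective therefore rests on a descriptive mean, SD and range without an interval.

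The insensitivity of the tests is exact. The rejection rates and half-widths rest on assumed n and SD and do not measure this trial's loss. For ATD PA the finding is narrower: phase 9, read literally, and Data analysis disagree on whether a baseline comparison is made. Confidence is medium, because Table 1 is not in the text at hand and the phase 9 wording admits two readings.

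**What to change.** 1. In phase 9, limit the comparison with the initial assessment to FIM, the mobility scales and any other instrument with a comparable baseline. Make phase 9 and Data analysis say the same about ATD PA.
2. In Data analysis, state the main PIADS analysis as the 6-month mean with 95% CI. Add the 2-month estimate and the paired change from 2 to 6 months as support. If the instrument has a defined no-impact value, state it and read the interval against it; a one-sample t or Wilcoxon signed-rank test is optional.
3. In the sentence on dichotomous variables, replace the paired t-test with the independent-samples t-test. Label PIADS subgroup tests and correlations as exploratory. They belong with phase 10, whose results "will allow to determine the influent factors that would be able to facilitate or restrict the good and efficient use of this device".

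The cost is wording only. The PIADS data at 2 and 6 months are already planned, and no visit, instrument or participant is added.
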